# **Effects of caffeinated gum on a Batting and Pitching Performance of Female Softball Players: a crossover trial**

**Document Date: May 22, 2022**

## **Project summary**

The purpose of this study was to investigate the effects of caffeinated chewing gum on female softball pitching and hitting performance. 24 trained female softball players (10 pitchers and 14 fielders) were divided into a caffeine chewing gum trial (CAF) or a placebo trial (PLA) in a single-blind, randomized, crossover experimental design. Two pieces of gum containing 100 mg of caffeine (CAF) or without caffeine (PLA) were chewed for 10 minutes and then spit out, followed by a 15-minute warm-up. The physical tests included grip strength and countermovement jump. The softball-specific tests included pitching (fast ball speed) or hitting (exit speed). The two trials were separated by seven days.

## **Introduction**

Women's softball is one of the most popular sports in the world and a summer Olympic sport. For softball performance, pitching and hitting performance are important factors that affect the game. Pitching velocity is an essential factor in evaluating pitching performance. Factors affecting ball velocity include upper extremity muscle strength and lower extremity explosive power (1, 2). Muscle strength and explosive power not only improve ball velocity but also improve ball control (3). For hitting performance, bat-swing speed and exit speed are essential indicators of batting ability. Faster bat speeds allow for more reaction time and quicker exit speeds (4), which in turn allows the ball to be hit farther and makes it more difficult for the defense to handle the ball (5), resulting in an increased chance of scoring runs. In

addition to bat selection (6), factors affecting bat speed include lower body strength (6, 7) and trunk rotation (8) (9) (10). Therefore, enhancing muscle strength or explosive power may significantly affect the specialized performance of women's softball pitchers and batters.

Caffeine (1, 3, 7-trimethylxanthine) is a plant-derived chemical commonly found in the daily diet, including coffee, tea, and energy drinks. Caffeine acts on the central nervous system, antagonizing adenosine and increasing the concentration of neurotransmitters, including serotonin, dopamine, and acetylcholine, which have a stimulating effect (11, 12). In addition, caffeine improves the ability of the sarcoplasmic reticulum to release calcium ions and increases the availability of calcium in myofibers, improving muscle strength (13, 14). Caffeine supplementation before exercise has been confirmed effective in increasing maximal muscle strength and explosive performance (15). The increase in strength and explosiveness may have enhanced women's softball specialized performance.

Caffeine chewing gum is a convenient and effective way to get caffeine because of its fast absorption and bioavailability advantage. In a previous study, the relationship between the duration of chewing, the percentage of caffeine released, and the concentration of caffeine in plasma was investigated. It was found that chewing gum containing 100mg of caffeine for 5 minutes released 76% of the caffeine, and 96.2%

was released when chewing for 10 minutes. On the other hand, the caffeine concentration in blood plasma peaked at 10 minutes and 45 minutes. This means that caffeine is efficiently delivered and absorbed through the capillary in the oral mucosa. Some caffeine is swallowed through saliva and reabsorbed through the gastrointestinal tract (16). Ingesting chewing gum containing 100mg-300mg of caffeine 5-15 minutes before exercise has also been shown to improve exercise performance, such as vertical jump height, repetitive sprinting ability, power output, cycling time trial (17).

Whether ingesting caffeine chewing gum effectively enhances sport-specific performance in women's softball remains unclear. To accurately quantify the pitching ability of women's softball pitchers and the hitting ability of batters, we used a device with Doppler Radar and a high-speed camera [18] to investigate the effects of ingesting caffeinated chewing gum on the women's softball pitchers' and batters' performance. We hypothesize that ingesting caffeinated chewing gum can improve pitching and hitting performance.

## **Materials and methods**

### **Experimental design**

This study utilized a randomized, crossover, single-blind experimental design. At least two familiarization tests were conducted one week before the formal trial to ensure

each participant was familiar with the experimental procedures. Before the first formal trial, participants were randomly assigned to either the caffeinated chewing gum trial (CAF) with 200 mg of caffeine or the placebo trial (PLA) without caffeine, seven days apart (Figure 1). The primary outcome was the pitching and hitting performance, and the secondary outcomes were hand grip strength and height of countermovement jump.

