### **Pitching Performance**

The windmill pitching method was used in the pitching performance test. Using the adult women's fastpitch rules, the pitching plate is placed 13.11 meters from the home plate. A green screen is placed behind the home plate, and the location of the tape is marked. The player is asked to throw each ball to the target location. Each set consisted of 10 fastballs, three sets in total. Pitching data were collected and analyzed using Rapsodo Pitching 2.0 (Rapsodo Baseball System, Rapsodo Inc, Fisher, IN). This device has been used in the literature and has been found to have high reliability for both hitting and pitching measurements (24, 25). During the test, the device was placed 15.6 feet from the front edge of the home plate according to the manual to ensure data accuracy. The pitching test evaluates average and maximum fastball velocity and average fastball spin rate.

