### **Hitting Performance**

Hit off Tee was used in the hitting performance test. The T-base is placed on the front edge of the center of the home plate, adjusted to the height of the participant's navel, and set up the stance consistently. A target is set 10 meters in front of the home plate at a height angle of 10 degrees, requiring the participant to hit each ball to the target position. There were five sets of 5 swings per set. Hitting data were collected and analyzed using Rapsodo Hitting 2.0 (Rapsodo Baseball System, Rapsodo Inc, Fisher, IN). During the test, the device was placed 14 feet from the front edge of the home plate according to the instruction manual to ensure data accuracy. The batting test evaluates average exit speed and maximum exit speed.

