### **Statistical analysis**

Data from this study were presented as mean  $\pm$  standard deviation and analyzed using SPSS 23.0 statistical software. The Shapiro–Wilk test was conducted to test the normality of the data. Paired samples t-tests were used to compare hand grip strength, countermovement jump, average exit speed, max exit speed, average fastball speed, max fastball speed, and average fastball spin rate. The significance level was set at  $\alpha < 0.05$ .

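### The primary outcome names a domain, not a measure: five pitching and hitting variables are each tested at 0.05 and none is designated primary

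*Protocol*

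**What the plan says.** Experimental design sets the hierarchy of outcomes in one sentence: "The primary outcome was the pitching and hitting performance, and the secondary outcomes were hand grip strength and height of countermovement jump".

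The content of the primary domain is given under Outcome Measure:

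- Pitching Performance: "The pitching test evaluates average and maximum fastball velocity and average fastball spin rate". The shots are described as: "Each set consisted of 10 fastballs, three sets in total", which makes 30 pitches per session.
- Hitting Performance: "The batting test evaluates average exit speed and maximum exit speed". Here "There were five sets of 5 swings per set", which makes 25 swings per session.

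Statistical analysis applies paired t-tests to grip strength, jump height and "average exit speed, max exit speed, average fastball speed, max fastball speed, and average fastball spin rate". One significance level, 0.05, covers all seven tests. No test is marked as primary, and no order or adjustment is given.

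Two other places narrow the field without settling it. The Project summary mentions only fastball speed for pitching and exit speed for hitting. The Introduction says "Pitching velocity is an essential factor in evaluating pitching performance" and treats exit speed similarly for hitters. Neither place chooses between average and maximum, and neither mentions spin rate. The hypothesis that closes the Introduction is worded at the level of the domain.

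**The concern.** A primary outcome has to identify the variable whose result will be read as the answer. Here the candidates are listed but the choice among them is not made. If average and maximum speed give different verdicts, or only spin rate moves, the protocol does not say which result carries the primary claim, so the choice can follow the data.

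This is not merely detail awaiting a SAP. Alpha allocation can be left to a SAP, but this protocol itself fixes the primary outcome, the variables, the tests and the significance level. Followed as written, it leaves the main claim undefined. At stake is the false-positive rate behind any statement that the gum improved pitching or hitting.

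**Working it through.** The protocol gives no power calculation or family-wise error rate, so there is no planned figure to reproduce.

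**Inputs from the protocol.** 10 pitchers, three measures, 30 pitches per session; 14 fielders, two measures, 25 swings per session; 0.05 for each test. **Assumed.** Two-sided tests (the protocol does not say), and all correlations between measures (none is given).

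**Step 1. Independent measures.** The chance of at least one false positive among k tests is 1 − 0.95^k.

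- Two speed measures: 1 − 0.95² = 9.75% per cohort.
- Three pitching measures: 1 − 0.95³ = 14.3%.

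**Step 2. Correlated measures.** Average and maximum come from the same shots, so independence is an upper case. Simulated paired t-tests for two speed measures give 7.2% at r = 0.9 and about 5.8% at r = 0.99, falling to 5% in the limit.

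**Step 3. A model tied to the planned shots.** Assume normally distributed shots, the maximum as the best single shot, and a session-to-session shift whose SD is 0.25 to 2 times the shot SD. For the pitching column that adds spin rate, its within-player difference is assumed to correlate 0.3 with that of average speed. Under no caffeine effect:

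| Shift SD / shot SD | 0.25 | 0.5 | 1 | 2 |
|---|---|---|---|---|
| Pitching: r, average with maximum | 0.557 | 0.755 | 0.911 | 0.975 |
| Pitching: either speed measure significant | 8.9% | 8.1% | 7.2% | 6.2% |
| Pitching: either speed measure or spin rate | 13.3% | 12.5% | 11.6% | 10.6% |
| Hitting: r, average with maximum | 0.565 | 0.756 | 0.909 | 0.974 |
| Hitting: either speed measure significant | 9.0% | 8.2% | 7.2% | 6.3% |

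Counting only results that favour caffeine, the speed-only rates are 4.4% to 3.1% (pitching) and 4.5% to 3.2% (hitting), against a nominal 2.5%. If spin rate is much more closely tied to speed, the three-measure rate is lower: 8.8% with all r = 0.9.

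**Step 4. Disagreement when caffeine works.** In the same model, let caffeine shift every shot equally, by an amount that gives the average 80% power. The two verdicts then differ in 49%, 29%, 13% and 6% of trials (pitching) and 48%, 29%, 13% and 6% (hitting). Split by direction, the maximum succeeds where the average fails in only about 2 to 3% of trials. The rest is the noisier maximum failing: the SD of its within-player difference is 1.03 to 1.8 times that of the average. Free choice between them raises power from 80% to about 82 to 83%.

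**Step 5. Detectable effects.** For a paired t-test, power is P(|T| > t(1 − α/2; n − 1)), with T noncentral t on n − 1 degrees of freedom and noncentrality d√n. Here d is the mean difference in units of the SD of the within-player difference. Solving for 80% power:

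| Cohort | d at 0.05 | First Holm step | d at first Holm step |
|---|---|---|---|
| Pitchers, n = 10 | 0.996 | 0.05/3 = 0.0167 | 1.223 |
| Fielders, n = 14 | 0.810 | 0.05/2 = 0.025 | 0.914 |

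**The case against.** The strongest reply is that the harm is conditional and modest. The protocol nowhere says that one significant measure is enough; if all measures had to succeed, there would be no inflation. The Project summary and Introduction direct attention to speed, and average and maximum are closely related, so the realistic rates are nearer 6 to 9% than 9.75%. The 11 to 14% range needs spin rate to count as a success measure, which those two sections never suggest. All seven variables are listed openly, so omitting one from a report would show. Alpha allocation may be in a SAP that is not at hand. All of this stands as a limit on size. None of it supplies the missing choice: with spin rate set aside, average and maximum are still both open in each cohort.

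Three stronger readings are tempting and are not supported.

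- A reader might pool all five tests and quote 1 − 0.95⁵ = 22.6%. That assumes independence between measures taken from the same shots, and a single claim resting on any success in either cohort. The protocol supports neither.
- A reader might take the 49% disagreement as the harm of the open choice. It sits at one end of an assumed range and mostly shows that the maximum is the weaker measure; the gain from choosing freely is 2 to 3 percentage points of power.
- A reader might infer that the measures were picked after the results were seen. The document, dated May 2022, does report achieved baseline data (Participants) and gum-guessing results (Caffeinated chewing gum and Placebo), and it cites 2023 publications. That shows the text was at least partly written or revised later. It does not show that outcomes guided the choice, only that prior choice cannot be assumed.

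**Conclusion.** The point holds and should be fixed. The protocol fixes a primary domain of five variables, tests each at 0.05, and does not say which one decides. If any one significant measure is read as success, the two-sided false-positive rate per cohort is about 6 to 9% for the two speed measures. For pitching it is about 11 to 14% if spin rate is admitted. These figures rest on the shot-level model, the assumed shift range and spin correlations from 0.3 down to independence; the documents give no data to narrow them. At very high correlation the speed-only inflation nearly vanishes. The lack of a defined primary measure does not depend on any of these assumptions.

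**What to change.** **Unless a prior choice can be shown (the leading branch, given the achieved data in the document).** Amend Experimental design and Statistical analysis so that all five pitching and hitting measures are reported with mean difference and 95% CI. Apply Holm within each cohort, over three tests in pitchers and two in fielders, and label any single headline variable post hoc. Cost: the first-step detectable effect at 80% power rises from 1.00 to 1.22 SD (n = 10) and from 0.81 to 0.91 SD (n = 14).

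**If a choice made before outcomes were seen can be documented.** Name that speed measure for each cohort as primary in Experimental design, for example average fastball speed in pitchers and average exit speed in fielders, as two separate questions at two-sided 0.05. Make the remaining three measures secondary there and in Statistical analysis. Detectable effects stay at 1.00 and 0.81 SD. The average is the less noisy measure in the model above, but that model has caffeine shifting every shot equally, and an effect confined to the best effort could be missed. The chance of a false positive in at least one cohort is 1 − 0.95² = 9.75%, so no single overall claim should rest on either cohort alone.

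Both branches change wording in two sections and add no participants or measurements.

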## **Participants**

Twenty-four trained female softball players without the habit of caffeine intake were recruited in this study as participants. The participants included fourteen fielders (age  $20.3 \pm 1.3$  years; height  $159.5 \pm 5.2$  cm; body mass  $58.1 \pm 6.9$  kg; habitual caffeine intake  $37.4 \pm 10.2$  mg/day) and ten pitchers (age  $20.5 \pm 1.3$  years; height  $163.9 \pm 4.6$  cm; body mass  $68.0 \pm 6.7$  kg; habitual caffeine intake:  $26.3 \pm 6.5$  mg/day). Inclusion criteria are 1. adult female; 2. at least six years of professional softball training and familiarity with all softball skills; 3. caffeine intake of less than 80 mg daily. Exclusion criteria were: 1. not professionally trained; 2. having a medical condition for which exercise is not recommended, such as hypertension, hyperlipidemia, or heart disease; 3. having any musculoskeletal injuries within the last six months or not being able to complete a full trial; 4. having a history of caffeine allergy.

Participants were asked to avoid excessive training or vigorous exercise for 72

hours before each formal trial and avoid caffeine or alcohol for 24 hours before each test. At the time of recruitment, the purpose of the experiment, the complete procedure, and the potential risks were explained. Participants will read and sign the consent form to ensure they understand the entire process and their rights before the experiment. This study was approved by the Institutional Review Board of Jen-Ai Hospital - Dali Branch (111-22). This study follows the principles of the Declaration of Helsinki and the recommendations proposed by the CONSORT Statement.

### **Experimental protocol**

All participants are required to take a familiarization test at least two times before the official experiment to ensure that they are familiar with the experimental protocol. The formal trial includes grip strength, vertical jump, pitching, and batting tests. Before the first trial, the participants' diets for the previous two days were recorded, and the participants were asked to consume the same food before the next test, especially breakfast and lunch on the day of the trial. On the day of the experiment, participants were asked to fast for at least 3 hours and arrive at the lab at 3:30 p.m. All experiments were conducted at the same time each week.

When participants arrived at the laboratory, the first formal experiment collected basic information, including age, height, weight, and habitual caffeine intake. Then,

they were randomly assigned to either the CAF or PLA trials. During the formal experiment, a 5-minute break was taken upon arrival at the laboratory, followed by administering caffeinated chewing gum containing 200 mg of caffeine or the placebo gum without caffeine, which was chewed for 10 min and then spit out. 15-min standardized dynamic warm-up exercises were performed after the gum spat out, and the warm-up was conducted the same manner as during the daily training. Grip strength, vertical jump, and softball specialized tests were measured after the warm-up. After the first test, a second test was conducted at the same time one week apart, and the groups were switched to follow the same experimental protocol.

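### Does the protocol leave open whether each softball test rests on 24 players or on 10 and 14, and whether grip and jump are split by position?

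*Protocol*

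**What the plan says.** The Project summary describes the sample as "24 trained female softball players (10 pitchers and 14 fielders" and then says: "The softball-specific tests included pitching (fast ball speed) or hitting (exit speed". The Introduction links pitching ability to pitchers and speaks separately of "the hitting ability of batters".

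The Experimental protocol section lists the content of a session: "The formal trial includes grip strength, vertical jump, pitching, and batting tests". Later in the same section it says: "Grip strength, vertical jump, and softball specialized tests were measured after the warm-up". Neither sentence assigns a test to a position. The outcome sections do not do so either. Pitching Performance says "The player is asked to throw each ball to the target location", and Hitting Performance likewise refers only to the participant.

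The Participants section gives baseline data by position ("The participants included fourteen fielders", followed by the ten pitchers). The section on the gum and placebo gives the blinding check by position.

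The Statistical analysis section says "Paired samples t-tests were used to compare hand grip strength, countermovement jump" and continues with five softball variables, seven in all. It gives no number of players for any test and does not mention pooling or subgroups.

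**The concern.** Two things look wrong at first.

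The first is the 'or' in the summary against the 'and' in the procedure section. Pitching and hitting are the primary outcomes. If every player did both, each primary test would have 24 pairs. If position decided the test, pitching would have 10 and hitting 14. No section states the assignment outright, and eligibility does not settle it, because all players must know the full range of the game's skills.

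The second is that baseline data and gum guesses appear only by position. If that layout carried over to grip strength and jump height, which all 24 players perform on either reading, two secondary tests would become four. Each would rest on 10 or 14 pairs, and precision already available in the trial would be given away.

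**Working it through.** **Inputs.** The documents give 24 = 10 + 14 players, a paired t-test and a 5% level. They give no sample-size calculation, effect size or standard deviation of the differences, so there is no planned figure to reproduce. Two-sided testing and the standardised differences d (mean difference divided by the SD of the within-player differences) are assumptions, and d is shown as a range.

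**What the number of players is worth.** Power is the probability that a noncentral t variable with n − 1 degrees of freedom and noncentrality d√n exceeds t(0.975, n − 1). The half-width of the 95% interval, in SDs of the differences, is t(0.975, n − 1)/√n.

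| n | half-width | d for 80% power | power at d = 0.3 | 0.5 | 0.6 | 0.8 | 1.0 |
|---|---|---|---|---|---|---|---|
| 24 | 0.422 | 0.60 | 29% | 65% | 80% | 96% | 99.7% |
| 14 | 0.577 | 0.81 | 18% | 41% | 55% | 79% | 93% |
| 10 | 0.715 | 1.00 | 13% | 29% | 40% | 62% | 80% |

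Against 24 players, the interval is 0.577/0.422 = 1.37 times as wide with 14 and 0.715/0.422 = 1.69 times as wide with 10. The difference would be material if the plan really left the choice open.

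**Does it leave the primary tests open?**

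1. The sentence in Experimental protocol has the trial as its subject, not the player. It is an inventory. The reference to all participants stands in the sentence before it, which concerns familiarisation.
2. The summary's 'or' comes shortly after the split into 10 pitchers and 14 fielders. A trial can include both tests while each player does one, so the two sentences are compatible.
3. The Introduction states the aim as pitchers' pitching and batters' hitting. This fits 10 and 14 better than 24 and 24.
4. A paired t-test uses the pairs that exist. Under this reading there are 10 pitching pairs and 14 hitting pairs, so the analyst has no further choice of n. The 14 pairs lacking for pitching (24 − 10) and the 10 lacking for hitting (24 − 14) are not precision thrown away, because those players were not meant to supply them.

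**Does it split grip and jump?** The Statistical analysis section names each outcome once, under one paired test, without subgroup wording. At face value that is one test per outcome in all 24 players: 2 secondary tests with a half-width of 0.422. The sections laid out by position contain baseline characteristics and gum guesses, and neither is an efficacy analysis. The rows for 14 and 10 in the table therefore do not describe the stated plan for these outcomes.

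**Would position as a factor help?** Each player is her own control, so her position cancels in the difference between her two sessions. A main effect of position leaves the treatment contrast unchanged. A treatment-by-position term would contrast 10 players with 14, and the protocol states no question that depends on it.

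**The case for a change.** The best case for a change is that who performs which test is a matter of trial conduct, which the protocol should fix and a statistical analysis plan cannot supply. A session might contain 30 pitches (three sets of 10), 25 swings (five sets of 5) or both. No sentence says that only pitchers pitch or that only fielders hit. The text never equates batters with fielders, and pitchers can also bat. The outcomes affected are primary, and one sentence would settle it.

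Part of this stands: the assignment has to be inferred and is nowhere stated. But the inference draws on the summary and the Introduction together, and no passage says the opposite. Stating it would record what the text already implies and would not alter any of the seven tests.

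On grip and jump, the objection rests on layout alone. The analysis set for a secondary outcome is also something a protocol commonly leaves to the statistical analysis plan, which is not at hand here.

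**Conclusion.** The concern does not hold as a defect of the plan. The protocol is loosely worded about who performs which softball test, but it does not contradict itself. The natural reading is pitching in the 10 pitchers, hitting in the 14 fielders, and grip strength and jump height tested once each in all 24.

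The arithmetic is right: the difference detectable with 80% power is 0.60, 0.81 and 1.00 SD of the differences for 24, 14 and 10 players. For grip and jump, that loss attaches to a split the plan does not state. For pitching and hitting, the smaller numbers follow from the design and are not a choice left to the analyst. Adding position to a within-player comparison brings little or nothing.

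This rests on reading the session list as an inventory and on the Statistical analysis section meaning one test per named outcome. A sentence naming the players and the number behind each test would be tidy, but no result depends on it when the plan is followed as written.
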